- Study design will be in a prospective cohort trial. The first cohort will be patients who are having a cesarean section with OB/GYNs that prefer using paper bandages in patients with BMI <40 and prophylactic wound vacuum therapy in patients with BMI > or = 40. The second cohort will be patients who are having a cesarean section with OB/GYNs that prefer using Mepilex Border Post-Op Ag regardless of BMI.
- This will be a pilot study as infection rates are low enough that a full study would take several years. However, if difference between methods are large enough then the study would be able to reveal this (see sample size section for details)
- There will be two cohorts:

- 1) Cohort 1 - Normal risk (BMI < 40) – standard dressing (sterile gauze dressing)
High risk (BMI > or = 40) – negative pressure wound therapy / "wound vac"
- 2) Cohort 2 - Normal risk (BMI < 40) – silver impregnated silicone dressing
High risk (BMI > or = 40) – silver impregnated silicone dressing

b. Population

i. Inclusion/Exclusion Criteria [See Human Subjects items to be moved here]

- Inclusion/exclusion criteria: pregnant women who have a cesarean section; as the bandage will be applied when women are no longer pregnant (after fetus is delivered) they will technically not be pregnant at the time of inclusion in the study
- Women will be excluded from the study if their bandage / BMI are not compatible with the cohort scheme noted above (for example if the patient's OB/GYN uses a bandage that is different than a wound vac, paper bandage or Mepilex dressing).
- Specific diagnosis & procedure codes – pregnancy, cesarean section not having other abdominal surgery (example: concomitant hernia repair) except for with concomitant bilateral tubal ligation, which is often done with cesarean sections
- Specific demographic inclusion/exclusion criteria – women of child bearing age having cesarean section at Régions Hospital
- We will compare patients to a database of patients who have asked to be excluded from research, we will exclude patients who requested this. This information is kept in central HealthPartners databases.

ii. Sample size

- Sample size of records to be obtained – enrollment will be 2 years, 1000 women
- Sample size for the main analysis – anticipated follow-up of 75%, which would net 750 women

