- A rationale for selecting the sample size is provided and is summarized as due to a 0.5-3% post-operative infection rate in order to adequately power a study to find a difference – the records to be obtained would include all patient who satisfy the inclusion criteria, approximately 500 per year. Based on this study population and anticipated surgical site infection rate of 0.5% in best case scenario and 3% (both better than the national mean) with a power of 80% and alpha 0.05 we would need a study size of 862. As this is the first study of its kind in the comparison groups it would be clinically salient to find significance or not find it as both results would be clinically helpful in guiding obstetricians.
- Follow-up in the postpartum period is notoriously low, approximately 50%. After cesarean most women tend to at least follow-up for an incision check in the clinics or go to the emergency room and thus it would be reasonable to expect 75% follow-up based on author prior clinical experience.
- Counts of patients expected to be study-eligible are approximately 500 / year based on our standard variation in annual cesarean rates.
- Our two cohorts should be of similar size. Approximately half of the OB's have chosen each closure method as their method of choice. All surgeons have similar obstetric volume and so the total group sizes will likely be similar in size. There are no anticipated changes to the current practice over the next two years.

c. Data collection process

i. Process steps for identification of patients or records

- We will use obstetric logs (paper log), MIDAS (electronic log) and hospital/clinic EMR to identify any women who have a cesarean section at Regions hospital in the date window of interest.
- The PI and co-investigators will review the patient records in the bullet points above for surgical site infection. Currently the Infection Prevention department already does this; the charts of the patients identified will be abstracted. All patients in the study will have their charts abstracted as

well by the PI for suggestion of surgical site infection or for any potential complications related to the surgical site coverings (standard gauze bandage, silver impregnated silicone dressing or negative pressure wound therapy device). Any question will be reviewed by an additional co-investigator obstetrician; if there is a discrepancy then the third co-investigator will make a final determination.

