Descriptive statistics generally as mean or total; chi-squared, Students t-test, Fisher exact tests as appropriate. Regression may be difficult with low infection rates.

- Anticipate roughly 300-600 participants per cohort (after accounting for patient follow-up)
- Variables per section "E" above
- Silver impregnated silicone dressing versus wound vac/paper dressing will be 1 study analysis. Then stratification by arm will be completed
- Infection rate will be reported as number (proportion). Clinical significance will be $P<0.05$. Dichotomous/categorical data will be reported as a proportion. Continuous variables may be dichotomized versus kept as a scale depending on the analysis (for example in our $BMI > or = 40$ versus $BMI <40$ would be one example of dichotomized data). Hemoglobin a1c (a measure of diabetic control) would likely be dichotomized into <7 (preferred in pregnancy) versus >7 .
- Missing data will be analyzed on a per-participant basis—for example if there is a recent BMI and not one done the day of surgery that may be used. Missing data that is used will be reviewed by a second investigator for appropriateness, if not certain then a third investigator will opine as to the appropriateness as a tie-breaker.
- We will obtain hospital / practice billing data averages (for patient care in general) to multiply by the additional visits (ER, home healthcare or clinic), admissions, procedures and surgeries to increase the clinical salience of our analysis.
- [name] wrote the analysis plan and will complete the analysis plan. SPSS v25 or similar will be used. A statistician from the HealthPartners Institute Research Methodology Group will be used for post hoc analysis for additional insight. [name] is confident he can complete descriptive as well as analytic statistics based on prior studies. He has generally performed his own statistical analysis when performing original research; post hoc statistician analysis has been consistent with his findings in these studies.

f. Power analysis or statement of precision

The following study parameters were used to find an appropriate sample size:

Study Parameters:

Incidence, group 1:	0.5%
Incidence, group 2:	3%
Alpha:	0.05
Beta:	0.2
Power:	0.8

The following sample sizes would be needed to have adequate power with a dichotomous endpoint, two independent sample study:

Sample Size:

Cohort 1	431 (silver impregnated silicone bandage)

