Cohort 2	431 (negative pressure therapy, sterile gauze bandage – composite)
Total	862

The study might be underpowered to demonstrate the hypothesis when comparing the cohorts. Unlike certain interventions a positive or negative difference would be clinically salient as the groups have significantly different costs. Thus regardless of outcome this study could help our group modify practice.

g. Strengths and limitations

A strength of the study is the relatively homogenous environment in which the study will be conducted. While this also would decrease applicability to the general field of obstetrics it increases power to find differences where they might be too difficult to find otherwise. This includes a single hospital with a group of obstetricians that are all willing to participate in conducting this study (based on administrative meetings where we committed to studying a change in our practice prior to completely implementing it). Additional strengths include that this will be the largest trial of its kind and rather than studying an intervention against an outdated method we are comparing three specific interventions in a head-to-head trial (in two cohorts). An additional strength of this study is that our Infection Prevention co-investigators already collect much of the information in this study and have a robust system to detect surgical site infections that are noted outside of our system. A final benefit of this study is that it is able to incorporate two state-of-the-art interventions already being done that are low-risk and demonstrate which has the lowest complication rate to help inform our practice and the field of obstetrics in clinical care. In adding cost data to this analysis we will also help providers and hospitals maintain their fiduciary duties.

- Limitations are primarily related to our sample size; unfortunately it is not possible in our practice to increase enrollment numbers without extending the study by several years; while this could be done it would not anticipated. Another limitation (despite being a strength) is that our practice is rather homogenous and so generalizability to other practices may be limited; as this would be the only data of its kind, this should at least help spur further research.

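### The main analysis is sized on women who return after discharge; if infected women return more often, infection rates are inflated, and the comparison is biased if that selection differs by cohort

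*Combined protocol and SAP*

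**What the plan says.** Section 4.b.ii gives two counts. The first is "Sample size of records to be obtained – enrollment will be 2 years, 1000 women". The second, for the main analysis, is "anticipated follow-up of 75%, which would net 750 women". Section 4.e sizes the cohorts on the same basis: "Anticipate roughly 300-600 participants per cohort (after accounting for patient follow-up".

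The text supporting the 75% shows what follow-up means: after a cesarean, "most women tend to at least follow-up for an incision check in the clinics or go to the emergency room". The 75% itself rests on clinical experience.

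Other parts of the plan bear on the choice of denominator:

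- The eligibility criteria in section 4.b.i do not require follow-up, and no section defines an analysis set.
- Section 4.c.i has every study patient's chart abstracted and checked against the Infection Prevention department's register. Section 4.g adds that the co-investigators in that department "have a robust system to detect surgical site infections that are noted outside of our system".
- The third data form in section 4.d records follow-up after discharge as yes or no, separately from enrollment.
- Section 3 gives the current infection rate as 4 to 10 per 500, or 0.8 to 2%, with all annual cesareans as denominator.
- The missing-data rule in section 4.e works case by case. Its only example is a missing BMI.
- The list of possible biases in section 4.g does not include loss to follow-up.

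**The concern.** A clinic or emergency room visit happens after surgery and can be prompted by the outcome itself. A woman with drainage or redness has a reason to come back that a woman with a clean incision lacks. Restricting the analysis to women who were seen would then keep most infections and lose some uninfected women from the denominator.

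Two consequences follow. The absolute rates would be too high and could not be set against the plan's own baseline, which counts every cesarean. And because the cohorts are formed by surgeon preference, any difference between surgeons or clinics in bringing women back falls on the cohort comparison. The plan has no table of follow-up by cohort and no sensitivity analysis that would reveal this.

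**Working it through.** **The plan's own figures.** Inputs from sections 4.b.ii and 4.f: 0.5% versus 3%, alpha 0.05, power 80%. Sidedness is not stated; the two-sided pooled formula without continuity correction matches.

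n = [1.960 × √(2 × 0.0175 × 0.9825) + 0.842 × √(0.005 × 0.995 + 0.03 × 0.97)]² / 0.025² = 430.7, so 431 per cohort and 862 in total, as stated. Also 1000 × 0.75 = 750, or 375 per cohort if the cohorts are equal.

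**Inflation of the rate.** Let p be the true rate, r the share of infected women who return and f the overall share who return. The rate among followed women is p × r / f, so the inflation factor is r / f. The plan gives f = 0.75. It gives no r, so a range is assumed:

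| r (assumed) | Factor at f = 0.75 | True 1% appears as | True 2% appears as |
|---|---|---|---|
| 75% | 1.00 | 1.00% | 2.00% |
| 90% | 1.20 | 1.20% | 2.40% |
| 100% | 1.33 | 1.33% | 2.67% |

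**Against the baseline.** If all of the 4 to 10 infections per 500 were among followed women, the same infections over 375 women would give 4/375 = 1.07% to 10/375 = 2.67%, against the quoted 0.8 to 2%.

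**Effect on the comparison.** With equal true rates, the apparent relative risk is (r₂/f₂) / (r₁/f₁). It equals 1 when return is unrelated to infection (r = f in each cohort), however much follow-up differs, and also when r/f is the same in both cohorts.

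For an illustration, assume that all infected women return and that uninfected women return with probability g. The observed rate is p / [p + g(1 − p)]. With p = 1.5%:

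- g = 0.85: 0.015 / (0.015 + 0.83725) = 1.76%
- g = 0.65: 0.015 / (0.015 + 0.64025) = 2.29%
- apparent relative risk: 2.29 / 1.76 = 1.30

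The same mechanism in terms of overall follow-up, with all infected women returning and a true rate of 2% in both cohorts:

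| Follow-up by cohort (assumed) | Apparent relative risk | Chance of Fisher P<0.05 |
|---|---|---|
| 75% / 75% | 1.00 | 3.1% |
| 80% / 70% | 1.14 | 4.5% |
| 85% / 65% | 1.31 | 7.8% |
| 90% / 60% | 1.50 | 12.8% |

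**The all-women denominator, tested in the same way.** Suppose return is 85% versus 65% but unrelated to infection, the true rate is 1.5% in both cohorts, and infections in unseen women are missed. Followed women then give 1.5% in both cohorts. All women give 1.5% × 0.85 = 1.28% versus 1.5% × 0.65 = 0.98%, a false relative risk of 0.85/0.65 = 1.31.

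**Power for 0.5% versus 3%.** With all infections captured, power is 85.8% with 375 followed women per cohort (apparent rates 0.67% versus 4.0%) and 85.5% with all 500. With 75% of infections captured, it is 74.3% and 74.1%. The choice of denominator makes almost no difference.

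**The case against.** The strongest reply is that the restriction is only a planning count. It appears in the sample-size text and the expected cohort sizes; the eligibility criteria do not impose it, every chart is abstracted, and follow-up is recorded as a variable. A reader might infer that the plan formally excludes unfollowed women, and the documents do not go that far. But section 4.b.ii does label the 750 as the main-analysis sample, no other denominator is named, and an analyst following the text would use it.

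A second reply is that neither return by infection status nor return by cohort is given. Section 4.c.ii describes routine care and the same wound instructions for every group. This stands: the 1.30 is an assumed illustration, and a reader who concludes that unequal return alone biases the comparison goes too far.

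A third reply is that counting every woman has its own bias. This also stands. A reader might take section 4.g to mean that infection status is known for everyone, but it covers infections that some provider noted. The definitions in section 4.d rest on clinical findings, so a woman seen nowhere has no observed status. As shown above, missed cases can distort the comparison as well as lower the rates.

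Finally, the figure of about 50% in section 4.b.ii describes postpartum follow-up in general, in contrast with the 75% expected after cesarean. It should not be used as this plan's expectation.

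**Conclusion.** The point holds as a risk of selection bias from an undefined denominator. If infected women return more often than others, rates among followed women are inflated by at most 1.33-fold at 75% follow-up and are not comparable with the all-cesarean baseline. The cohort comparison is biased only if return depends on infection and the resulting selection also differs by cohort; the relative risk of 1.30 shows the size under stated assumptions and is not a prediction.

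Two further inferences are tempting and are not supported. One is that analyzing all 500 per cohort gains power: for the same captured infections, power is essentially unchanged. The other is that the cost per infection avoided would be overstated. With all infected women returning at 75% follow-up, the risk difference grows from 2.5 to 3.3 points, so for a given cost difference that ratio would fall to 2.5/3.33 = 0.75 of its value. In any case, section 2 plans comparisons of practice costs and total cost of care, not that ratio.

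**What to change.** State in section 4.e that the primary analysis set is all eligible cesareans, with infection within 30 days taken from chart abstraction plus the Infection Prevention register. Bring the 750 in section 4.b.ii and the range of 300 to 600 in section 4.e into line with it; 600 in both cohorts would exceed the 1000 records. Then add:

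- a table of follow-up by cohort and BMI stratum, from the field already on the third form;
- the followed-women-only analysis as a sensitivity analysis;
- best-case and worst-case bounds for women without follow-up. About 125 of 500 women per cohort would be unseen at 75% follow-up, so counting all of them as infected could add up to 125/500 = 25 points. The extremes should therefore be accompanied by a graded range of assumed infection rates in unseen women, varied separately by cohort;
- loss to follow-up in the list of biases in section 4.g.

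The cost is SAP wording and a few tables, with no new data collection. The downside is that infections never noted by any provider count as none. This lowers the rates and can distort the comparison if capture differs by cohort, which is why the bounds belong in the plan.

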
2. Study aims

- Our research question is which of our current practices of covering cesarean section incisions is 1) most clinically effective at eliminating surgical site infection and 2) is most cost effective. Patient safety is paramount and we would want to use the most effective form of surgical site infection prevention bandage/covering – however we do not know which of our practice is more effective. This question is unique to both high risk patients (BMI = or > 40), which uses one type of covering versus our normal risk patients (BMI < 40).
- Our hypothesis is that a sterile silver impregnated silicone foam dressing (Mepilex Border Post-Op Ag) will be effective in maintaining a low surgical site infection rate in both high risk patients (BMI = or > 40) as well as in normal risk patients (BMI < 40). We believe using the Mepilex bandage will be a more cost effective strategy.
- Post-operative surgical site infections are uncommon in our practice (about 1%) they are clinically and financially significant complications of surgery. Strategies to minimize this known complication are essential. Our study is largely exploratory in that there aren't any adequate head-to-head studies that can help us guide our practice in selecting a wound-cover following cesarean.
- The primary clinical aim of this project is to compare and differentiate infection rates between our current two practices. The first practice that many of our OB/GYNs have selected (as part of their clinical practice, not this study) is prophylactic negative pressure wound therapy dressing (wound vac) in high risk patients (BMI = or > 40) and a standard sterile dressing in women who are normal risk (BMI < 40). This change in addition to our surgical site bundle have shown dramatic decreases in surgical site infections and many of our doctors want to continue

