- Patient's will be informed via standard HealthPartners methods, which includes potential inclusion in research unless they request to be excluded.

Who will provide consent? We will ask for a waiver of informed consent.

How will you ensure that the subject understands the consent? We will apply for a consent waiver. In an opt-out manner if a patient requests to not be included we will respect the patient's privacy in making this decision as part of standard HealthPartners policies.

d. Outcome/endpoint and other variable definitions, and instruments used

Definitions: superficial surgical site infection- defined according to Centers for Disease Control and Prevention criteria as infection involving only the skin or subcutaneous tissue occurring within 30 days of surgery with at least one of the following: 1) purulent drainage from the wound or 2) organism identified by culture or wound deliberately opened by the surgeon. Cellulitis will be evaluated as 1) erythema noted in clinical progress notes with antibiotics administered or 2) diagnosis of cellulitis with antibiotics administered. Our secondary outcome was a composite wound complication, including superficial, deep, or organ-space surgical site infection; wound dehiscence; seroma; or hematoma that occurred within 30 days of surgery. Other secondary outcomes included 30-day readmission, 30-day reoperation, and need for antibiotic treatment for any indication. The chart will be evaluated for nursing or provider notes that indicate problems with the bandage. Chart abstraction will be completed to look for other salient complications or factors that were not predicted. Primary and secondary outcomes will be binary with comments possible. Number of clinical visits for complications, enrollment in home healthcare for wound care and length of hospital visits will be noted.

Chart review form will be electronic, it will have the following elements (there will be 3 charts to protect PHI and to blind the analyst from the intervention), all participants will have a study enrollment number to link the data for appropriate analysis:

First form:

MRN	From EMR
Study enrollment #	From 1-1000

Second form:

Study enrollment #	From 1-1000
Intervention	Binary: cohort 1 vs cohort 2
BMI	BMI rounded to the tenths spot

Third form:

Study enrollment #	From 1-1000
Age	#
Enrolled	Yes / no
Follow-up after discharge from home	Yes / no
Complication noted	Yes / no
Date complication noted	Date

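### The superficial SSI definition lets deliberate wound opening count without any sign of infection, so an opening for seroma, hematoma or dehiscence can be coded as an infection

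*Combined protocol and SAP*

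**What the plan says.** Section 2 sets the clinical question: "The primary clinical aim of this project is to compare and differentiate infection rates between our current two practices". No sentence names superficial SSI as the primary outcome. It is, however, the main infection definition in Section 4.d, and the paragraph then turns to secondary outcomes.

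The stem reads "defined according to Centers for Disease Control and Prevention criteria as infection involving only the skin or subcutaneous tissue occurring within 30 days of surgery". At least one of two criteria must also be met. The first is "purulent drainage from the wound". The second is "organism identified by culture or wound deliberately opened by the surgeon". No local sign, symptom or treatment is attached to the second criterion.

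The next sentence, on cellulitis, does carry such a qualifier: it needs charted erythema or a diagnosis, and antibiotics must have been given.

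The secondary composite contains superficial, deep and organ-space SSI together with "wound dehiscence; seroma; or hematoma that occurred within 30 days of surgery". The chart form in 4.d lists seroma, hematoma and dehiscence as separate entries in the complication comment field. It also has fields for culture results, white counts and the indication for post-discharge antibiotics. It has no field for why a wound was opened or which SSI criterion was met.

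Section 4.c.i provides for adjudication: "Any question will be reviewed by an additional co-investigator obstetrician", and a third co-investigator settles disagreements.

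**The concern.** A wound may be opened to drain a seroma or hematoma, or because it has dehisced, with no infection present. Read as a checklist, criterion 2 is met by the opening alone. The plan gives no instruction that would send such a case to the composite only.

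Two features of this study raise the stakes:

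- Events are few. Section 2 puts the infection rate at about 1%, and Section 3 at 0.8-2%. A handful of misclassified wounds can change the comparison.
- Opening is the surgeon's decision, and the surgeon's dressing preference also determines the cohort (Sections 1 and 4.a). If the two groups of surgeons open wounds with different readiness, or if a dressing affects fluid collections, the counted infection rates could differ without any difference in infection. Section 4.e warns that regression may be difficult at these rates, so adjustment is unlikely to remove such a difference.

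Misclassification that is equal in both cohorts instead pulls the comparison toward no difference. The consent-waiver text hypothesises similar rates, and Section 6 says cost will be considered if no clinical difference is seen. Blurring would therefore favour the result that the investigators expect.

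**Working it through.** **Text.** Set the two adjacent definitions side by side. Cellulitis needs a sign or diagnosis and treatment. The opening limb of superficial SSI needs only the opening, under a stem that says infection. The plan does not say what in the chart establishes infection in an opened wound. That is the gap.

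**Inputs.** From Section 4.f: rates 0.5% and 3%, alpha 0.05, power 80%, 431 per cohort. From 4.b.ii: 750 women followed up, so 750 / 2 = 375 per cohort if the cohorts are equal. Assumed, because the documents give no figure: a false-positive rate m among women without true infection, from 0.25% to 2%.

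**Step 1: reproduce the plan's figure.** Two-sided pooled formula without continuity correction, with p̄ = 0.0175:

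n = [1.960 × √(2p̄(1−p̄)) + 0.8416 × √(p1(1−p1) + p2(1−p2))]² / (p2−p1)²

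= (0.3635 + 0.1554)² / 0.025² = 430.7, rounded up to 431 per cohort (862 in total). This matches the plan.

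**Step 2: add false positives equally to both cohorts.** Observed rate = p + m(1−p). For m = 0.5%: 0.005 + 0.005 × 0.995 = 0.998%, and 0.03 + 0.005 × 0.97 = 3.485%.

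Power = Φ{[(p2−p1)√n − 1.960 × √(2p̄(1−p̄))] / √(p1(1−p1) + p2(1−p2))}

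- At 431: (0.024875 × 20.761 − 0.4103) / 0.2086 = 0.509, so power is 69.5%.
- At 375: (0.024875 × 19.365 − 0.4103) / 0.2086 = 0.342, so power is 63.4%.

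| m (assumed) | Rate ratio | n per cohort for 80% | Power at 431 | Power at 375 |
|---|---|---|---|---|
| 0 | 6.0 | 431 | 80.0% | 74.3% |
| 0.25% | 4.3 | 493 | 74.5% | 68.6% |
| 0.5% | 3.5 | 555 | 69.5% | 63.4% |
| 1% | 2.7 | 680 | 60.6% | 54.7% |
| 2% | 2.0 | 935 | 47.7% | 42.6% |

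In women, m = 0.5% is about two wounds per cohort (431 × 0.5% = 2.2; 375 × 0.5% = 1.9).

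**Step 3: false positives in one cohort only.** Suppose the true rate is 1% in both cohorts and m = 1% in one. The observed rates are 1% and 0.01 + 0.01 × 0.99 = 1.99%. The chance of p < 0.05 in that direction is about 22% at 431 per cohort and 20% at 375.

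These are normal approximations. With so few events they show direction and rough size, not exact power.

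**The case against.** The strongest reply is that the definition starts with infection. Read plainly, a case needs an infection and one of the listed findings, so a clearly sterile seroma that was drained is not an SSI. This stands as far as it goes: the text does not make every opened wound an infection. It does not say how an abstractor decides that infection is present, so the decision falls to unwritten judgment.

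The plan also has safeguards. Doubtful charts go to a second and then a third obstetrician, cases are checked against the Infection Prevention register, and seroma, hematoma and dehiscence have their own entries. Together these make automatic miscounting unlikely. None is a rule for opened wounds, and the second review begins only when someone raises a question, which a literal reading of criterion 2 need not do.

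A reader might infer that SSI and the composite cannot be told apart, because one event feeds both. The documents do not support that. The composite contains superficial SSI by design, so overlap is expected under any definition, and the component entries let the two be separated. The weakness is only that a non-infectious event can enter the SSI count.

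Finally, nothing in the documents shows that opening practice differs between the cohorts. Section 4.g acknowledges ascertainment bias and argues that it falls after discharge. Differential error is therefore a possibility created by the design, not a finding.

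**Conclusion.** The concern holds in a limited form. The opening limb lacks a qualifier and an exclusion, so non-infectious openings can be coded as superficial SSI. They are not automatically so coded. The definition bears on the primary clinical aim, although superficial SSI is not itself labelled the primary outcome.

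The size is conditional. If 0.5% of women without infection were miscounted in both cohorts, power for the planned contrast would fall by about 10 to 11 percentage points. That is an illustration on an assumed rate. The true rate could be lower, including zero, or higher. The 431 per cohort does not change, since it rests on assumed infection rates.

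A reader might go further and infer that one third to two thirds of counted infections would be false: with 375 women, 1% gives 3.75 true cases, and 0.5-2% openings add 1.9 to 7.5. The documents do not support this. The opening rate has no source there, the sum assumes that every such wound is miscounted, and the recorded rate of about 1% may already include opened wounds.

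**What to change.** In Section 4.d, state that deliberate opening counts as superficial SSI only with charted evidence of infection: a local sign such as erythema, or antibiotics started for the wound. State that opening for seroma, hematoma or dehiscence without such evidence counts only in the secondary composite. A negative culture alone should not remove a case that has charted signs.

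Add one coded item to the chart form, for cases only, recording which criterion was met. Report the infection rate with and without opening-only cases.

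The cost is one or two sentences and one field. All charts are already abstracted under 4.c.i, and the form already takes culture results and the indication for post-discharge antibiotics. The change affects outcome classification only, not care. Its downside is a lower counted infection rate, and possibly a few true infections missed where signs were not charted. The paired reporting shows how much depends on the rule.
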